4.1 Inclusion Criteria

1. Adult patients with an American Society of Anesthesiologists (ASA) physiological status I-III
2. Patients presenting for unilateral primary total shoulder arthroplasty (includes anatomic and reverse total shoulder arthroplasty).
3. Patients 18 years of age and older
4. Able to provide informed consent for him or herself

4.2 Exclusion Criteria

- 1) Chronic pain syndromes such as fibromyalgia or complex regional pain syndrome
- 2) Chronic opioid use (>1 mos) with OME >5 mg/day OR acute opioid use (< 1 mos) with OME > 30 mg/day.
- 3) Body mass index (BMI) > 45 kg/m²
- 4) Severe drug allergy* to medications used in this study, including non-steroidal anti-inflammatory drugs (i.e. celecoxib and ketorolac), and local anesthetics.

- **defined as an immune reaction resulting in shortness of breath, hives, anaphylaxis, wheezing, and fever*
- 5) History of Malignant Hyperthermia.
 - 6) Major systemic medical problems such as:
 - Pre-existing severe renal disorder defined as glomerular filtration rate (GFR) <50 units/m² (if labs are available), currently on dialysis, or highly suspected based on history.
 - Severe hepatic disorder defined as current or past diagnosis of acute/subacute necrosis of liver, acute hepatic failure, chronic liver disease, cirrhosis (primary biliary cirrhosis), chronic hepatitis/toxic hepatitis, liver abscess, hepatic coma, hepatorenal syndrome, other disorders of liver
 - Pre-existing medical history of moderate to severe pulmonary disease (obstructive and/or restrictive), use of home oxygen, preoperative baseline oxygen saturation < 94% on room air, FEV 1 < 60% of predicted value (obstructive disease), VC or TLC < 70% predicted value (restrictive disease).³⁷
 - History of contralateral hemidiaphragm dysfunction (e.g., paralysis) or phrenic nerve injury.
 - 7) Contraindication to a regional anesthesia technique (e.g., preexisting neuropathy⁺ in the operative extremity, coagulopathy, sepsis, infection at site of injection, uncooperative, refusal, anticoagulation medications not held within appropriate time frame^{*}).
 - ⁺ *pre-existing neuropathy includes sensory and/or motor deficits due to nerve insult of surgical extremity, radicular symptoms of surgical extremity, history of unresolved brachial plexus injury/brachial plexopathy, and tumors of the brachial plexus. Patients with nerve compression distal to site of surgery, such as history of carpal tunnel syndrome or cubital tunnel syndrome, are NOT considered contraindications to regional anesthesia.*
 - ^{*} *Per ASRA guidelines, Clopidogrel (Plavix) held for at least 7 days, Dabigatran (Pradaxa) held for at least 5 days, Rivaroxaban (Xarelto) held for at least 3 days, Warfarin (Coumadin) held for at least 5 days or recent INR of less than 1.4, Enoxaparin (Lovenox) with doses > 1 mg/kg held for close to 24 hours.*³⁸
 - 8) Previous contralateral total shoulder replacement managed with regional anesthetic nerve block or periarticular injection/intraarticular injection within the previous 12 months.
 - 9) Known to be currently pregnant or actively breastfeeding⁺⁺
 - ⁺⁺ *Patients that have a previous history of menopause, hysterectomy, or tubal ligation will not be required to perform a pregnancy test. Female patients that do not meet this criterion will be asked to submit a urine sample, and will require a negative urine sample in order to proceed with study protocol. Urine sample be collected pre-procedurally.*
 - 10) Impaired cognition

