5.2 Treatment Regimen

As mentioned above in section 1.3, the LIA group will utilize weight based dosing of Ropivacaine as part of a "cocktail" solution (Table 1), and will receive a total volume of 120 mL injected in the periarticular structures by the surgeon. This is a one-time injection. This will occur after implantation of the final prostheses, but prior to closure of the fascia. All surgeons will complete the infiltration following a similar protocol, equally distributing the study medication around the glenoid and humerus, subscapularis, deltoid, posterior capsule and subcutaneous tissue. Medications and dosage of the LIA group is as follows:

Table 1: LIA Group

Drug	50-74.9kg	75-99.9 kg	100-125kg
Ropivacaine	200 mg	300 mg	400 mg
Epinephrine	100 mcg	200 mcg	300 mcg
Ketorolac	30 mg	30 mg	30 mg

*Normal Saline will be added to bring the total volume to 120 mL

SISB and CISB groups will utilize pre-mixed bupivacaine 0.5% with epinephrine 1:200,000 vial for the initial loading bolus. CISB group will have a continuous catheter attached to a pain pump infusing bupivacaine 0.2% when the patient arrives to the PACU.

Table 2 demonstrates the study medication for SISB and CISB groups.

Table 2: CISB and SISB Group – Bolus Injection

Nerve Blocked	Local Anesthetic	Concentration	Volume milliliters (mL)	- Adjuvants Added
Interscalene Brachial Plexus – CISB and SISB	Bupivacaine	0.5%	15 to 20 mL	1:200,000 Epinephrine

Please refer to section 6.2 for the SISB and CISB groups' technique and administration of local anesthetic.

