5.4 Preparation and Administration of Study Drugs

Please refer to section 5.2 with regards to treatment regimen and administration of the “cocktail” solution for the LIA group.

Pharmacy prepares the weight based dose Ropivacaine, Epinephrine, Ketorolac 30 mg, in Normal Saline 0.9% (for a total volume of 120 mL) and provides this to the surgical staff. The Department of Pharmacy follows United States Pharmacopeia (USP) <797> preparation standards.⁴⁰ In general, the pharmacy uses environmental engineering controls for air quality of the preparation area, personal protective equipment during compounding, and performs preparation within laminar flow hoods. This “cocktail” solution will be dispensed to OR personnel during the surgical procedure.

The pre-made “cocktail” solution will be placed in a sterile basin located on the operating room table, within the vicinity of the surgeon and operating room technician, who are scrubbed into surgery. Sterility includes a sterile environment such as the operating room, in which a sterile field is created utilizing sterile surgical drapes. Operating room personnel handling the study

solution will be in sterile gloves and surgical gowns, hats and masks, and standing close to the surgical field.

In the SISB and CISB groups, one vial of pre-mixed bupivacaine 0.5% with epinephrine 1:200,000 will be obtained from the anesthesia stock room. Solution is sterile and will be poured in a sterile fashion into the sterile nerve block tray.

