6.1 Pre-Operative Plan

Following informed consent and randomization, study staff will record baseline patient demographics (including baseline NRS values for pain at rest, age, weight, gender, ASA physical status) from the electronic medical record and/or during the patient interview.

NRS pain scores at rest will be measured at the following time points: arrival to post-anesthesia care unit (PACU), prior to PACU discharge, every 4 hours beginning on arrival to patient room. Pain scores will be measured until hospital discharge from the time of the initial assessment in

the recovery room (PACU). All NRS pain scores will be recorded by registered nurses per standard protocol.

Regional Block – Both CISB and SISB:

Based on our current total joint regional anesthesia pathway (MC1156-462rev0115 and MC1156-1321rev1015), all patients will be provided (unless contraindicated and at the discretion of the attending anesthesiologist) a combination of oral analgesic medications preoperatively:

- 1) Tylenol 1 gram – at least 6 hours since last dose
- 2) Celecoxib 400 mg – for patients 18-64 years old and CrCl > 50 mL/min (if lab is available)
- 3)
 - a. Oxycodone (immediate release)
 - i. 5-10 mg once for patients 18-64 years old
- 4) Scopolamine Transdermal patch: 1.5mg - Apply to skin behind ear for 24 hours for high-risk patients (history of motion sickness or postoperative nausea vomiting). This is at the discretion of the anesthesiologist.

Local Infiltration Analgesia (LIA):

- 1) Tylenol 1 gram – at least 6 hours since last dose
- 2) Celecoxib 400 mg – for patients 18-64 years old and CrCl > 50 mL/min (if lab is available)
- 3)
 - a. Oxycodone (immediate release)
 - i. 5-10 mg once for patients 18-64 years old
- 4) Scopolamine Transdermal patch: 1.5mg - Apply to skin behind ear for 24 hours for high-risk patients (Hx: motion sickness or postoperative nausea vomiting). This is at the discretion of the anesthesiologist.

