7.3 Subject Population(s) for Analysis

Our primary analysis will be performed based on the intention to treat. Therefore, any subject randomized into the study, regardless of whether they received study drug, will be included in the primary analysis. A subgroup analysis will also be performed on patients who received the allocated treatment as per the planned protocol, and patients undergoing reverse vs anatomic primary TSA.

8 Safety and Adverse Events

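### Table 1 defines an LIA dose only for 50 to 125 kg, but eligibility sets no weight limit, so an eligible patient can be randomised to LIA with no protocol-defined dose

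*Combined protocol and SAP*

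**What the plan says.** **Dose.** Section 5.2 states that "the LIA group will utilize weight based dosing of Ropivacaine as part of a" mixed solution set out in Table 1. The table is printed in Sections 1.3, 5.2 and 6.2 with the same bands each time: 50-74.9 kg, 75-99.9 kg and 100-125 kg. Ropivacaine and epinephrine change with the band; ketorolac and total volume do not. There is no open-ended band and no default row.

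**Preparation.** Section 5.4: "Pharmacy prepares the weight based dose Ropivacaine, Epinephrine, Ketorolac 30 mg, in Normal Saline 0.9"% saline. It gives no instruction for a weight outside the table.

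**Eligibility.** Section 4.1 asks for ASA I-III, unilateral primary shoulder arthroplasty, ability to consent, and "Patients 18 years of age and older". It has no weight criterion. In Section 4.2 the only body-size item is "Body mass index (BMI) > 45" kg/m². There is no lower BMI limit.

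**Comparators.** Table 2 gives the single-injection (SISB) and continuous (CISB) block groups the same bolus range whatever the patient's weight.

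**Order of events.** Section 5.3 describes no check of weight against Table 1 before the assignment is retrieved. Section 6.1 begins "Following informed consent and randomization, study staff will record baseline patient demographics", and weight is in that list.

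**Analysis.** Section 7.3: "any subject randomized into the study, regardless of whether they received study drug, will be included in the primary analysis".

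**The concern.** The eligible weight range is wider than the range with a defined LIA treatment, at both ends. A site that follows the plan exactly can randomise a patient and then have no row from which pharmacy can prepare the injection.

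Two things are at stake.

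- **Safety.** Local anaesthetic systemic toxicity (LAST) is the only technique-specific stopping criterion for LIA in Section 8.5. The block groups have a LAST criterion as well. Section 1.3 lists excessive dose among the causes of LAST, and Section 8.5 lists an appropriate dose among the preventive measures. For patients outside the bands, the protocol does not say what the dose is.
- **Symmetry between arms.** Whatever the site does with such a patient happens after allocation and only in LIA. A patient of the same weight allocated to SISB or CISB has a fully specified bolus.

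**Working it through.** **1. Upper end.** Weight = BMI × height². The BMI limit is 45 (Section 4.2) and the top of Table 1 is 125 kg. The two meet at height = √(125/45) = 1.667 m. Up to that height the BMI limit already keeps weight at or below 125 kg. Above it:

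| Height | Highest eligible weight (45 × height²) | BMI at 125 kg |
|---|---|---|
| 1.60 m | 115.2 kg | 48.8 (excluded) |
| 1.70 m | 130.0 kg | 43.3 |
| 1.75 m | 137.8 kg | 40.8 |
| 1.80 m | 145.8 kg | 38.6 |
| 1.90 m | 162.4 kg | 34.6 |

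**2. Lower end.** With no lower BMI limit, a patient under 50 kg is eligible at any height. For scale, 50 kg is a BMI of 50/1.50² = 22.2 at 1.50 m, 50/1.60² = 19.5 at 1.60 m and 50/1.70² = 17.3 at 1.70 m. The first two are unremarkable values in a small adult.

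**3. How many patients.** The documents give no weights or heights. Let p be the assumed share of enrolled patients outside 50-125 kg, with 43 in the LIA arm (Section 7.1). The expected number is 43p and the chance of at least one is 1 − (1 − p)^43.

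| p (assumed) | Expected of 43 | Chance of at least one |
|---|---|---|
| 1% | 0.4 | 35% |
| 2% | 0.9 | 58% |
| 5% | 2.2 | 89% |
| 10% | 4.3 | 99% |

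**4. Effect on the primary contrast.** First the plan's own figure. Section 7.1 uses a difference of 3, SD 3, 39 per group and two-sided alpha 0.017, and states power above 90%. By normal approximation the critical value is 2.387, the standardised difference is 3/(3 × √(2/39)) = 4.416, and power = Φ(4.416 − 2.387) = 97.9%. The plan's statement is reproduced.

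Now a pessimistic case: 4 LIA patients get no benefit from LIA and stay in the analysis, and the whole planned 3-unit difference depends on that benefit.

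- 43 per group: the difference becomes 3 × 39/43 = 2.72, and power = Φ(4.205 − 2.387) = 96.6%.
- 39 per group: the difference becomes 3 × 35/39 = 2.69, and power = Φ(3.963 − 2.387) = 94.3%.
- With the lowest relative efficiency of a rank test (0.864, multiplying the group size), these become 93.6% and 90.3%.
- Mixing treated and untreated patients also widens the spread in LIA. Its variance rises from 9 to 9 + (4/43)(39/43) × 9 = 9.76 with 43 per group, and to 9 + (4/39)(35/39) × 9 = 9.83 with 39. Power is then 95.8% and 93.2%, or 92.5% and 88.8% with the 0.864 factor.

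With one affected patient and 39 per group, the normal-approximation power is 97.2% against 97.9%. The CISB-SISB comparison is not touched in any of these cases.

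**5. Search for a rule that closes the gap.** The protocol states discretion where it intends it: the CISB infusion rate, failed-block management and PACU analgesia. It states none for the LIA mixture. Section 4.3 sends coordinators to the investigators with questions, but gives no dose and no reason to withhold randomisation from a patient who meets the listed criteria.

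**The case against.** The best case on the other side accepts the mismatch and disputes its consequences. Most of that case stands.

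- **Threat to the primary result.** A reader might infer that the gap undermines the intention-to-treat comparison. It does not. Section 7.1 already allows about 10% attrition, including failed blocks, and the pessimistic case above leaves power at about 94% to 97% by normal approximation. It drops just below 90% only when every unfavourable assumption is stacked.
- **A known share of patients.** A reader might put a definite figure on the share, for example by assuming a normal weight distribution. The documents support none. An upper tail taken from such a curve also ignores that the BMI limit already removes patients over 125 kg who are no taller than 1.67 m.
- **Weight unknown until after randomisation.** Section 6.1 might be read that way. Applying the BMI exclusion needs weight at screening, so Section 6.1 describes when study data are recorded, not when weight is first known. What is missing is a check of that weight against Table 1.
- **Termination, or loss from the per-protocol subgroup.** Section 4.4.1 concerns patients unable to comply, and stretching it to a missing table row is inference. Sections 4.4.2 and 7.3 do not say whether a clinician-determined LIA dose counts as treatment per the planned protocol. Selective loss of small or heavy patients from LIA is possible but not established.
- **An unsafe dose.** The documents show an unspecified dose, not an unsafe one. Investigators, pharmacy and surgeons who already use this mixture could resolve a case when it arises.

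The last argument does not dispose of the point. A route for asking is not a rule, and an answer found after allocation is still a deviation in one arm.

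**Conclusion.** The point holds as a mismatch between eligibility and the LIA dosing table. Patients under 50 kg at any height, and patients over 125 kg who are taller than about 1.67 m, can be randomised to LIA with no protocol-defined ropivacaine or epinephrine dose. This follows from the text and the BMI arithmetic alone.

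The number affected is unknown. About 0.4 to 4 of 43 LIA patients is conditional on an assumed 1% to 10% out of range. The statistical effect on the primary contrast is small, and the sample-size statement does not need to change. The reason to act is safety in an arm stopped for LAST, together with a source of deviations that falls on one arm and is easily removed.

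**What to change.** Reconcile Sections 4.1 and 4.2 with all three printings of Table 1, so that every patient who can be randomised has a defined treatment in each of the three arms. This can be done by making the eligible range and the table's range the same, or by having the clinical and pharmacy leads decide how the table covers the remaining weights. Which range or dose applies is their decision, and none is proposed here.

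Add to Section 5.3 a step that checks weight against the reconciled range before the allocation is retrieved. Any exclusion then applies equally to all three arms. No new measurement is needed, because weight is already required for BMI.

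The cost is one amendment and either a few excluded patients or a short pharmacy review.

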4.3 Subject Recruitment, Enrollment and Screening

After approval by Mayo Clinic IRB, we will work closely with the department of orthopedics at Mayo Clinic Hospital, Methodist Campus to enroll patients into the study. Potential subjects will consist of patients who present for elective primary TSA meeting the above inclusion and exclusion criteria (section 4.1 and 4.2). Subjects will be approached by study staff for

recruitment in person and informed consent will be obtained. Subjects unable to give consent themselves will not be approached for participation. No remuneration will be provided. All efforts will be made to enroll participants regardless of ethnic heritage. No passive recruitment methods (newspapers, advertisements, or flyers) will be used.

Research study coordinators will meet eligible participants at either their preoperative orthopedic appointment or the morning of surgery provided they are not the first surgical case of the day. A sufficient amount of time will be given to the patient to answer any questions he or she may have and to allow the patient to make a well informed decision.

Of note, study staff/clinical research unit, which includes the research study coordinators, is composed of RN's and RRT's. Given that this is an institutional initiated study, the study staff is able to enroll patients meeting all inclusion/exclusion criteria into the study. In the event that there are any questions or concerns, the study coordinators will contact the PI/Co-PI's.

Discussion of study participation will be conducted in a private room in the presence of the patient's family if he/she so desires. Information will be provided to the patient without any time pressure. Interruptions to this discussion will be minimized by holding this discussion after most of the necessary (not study related) preoperative patient care processes are completed. The study recruiter will be different from the care team. Patients will be reassured that participation in the study does not change in any way their care beyond the random allocation to one of the three intervention arms and subsequent data collection.

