5.3 Method for Assigning Subjects to Treatment Groups

The treatment allocation will be performed using a randomization schedule which will be created by the Division of Biomedical Statistics and Informatics. This randomization schedule will be generated using a SAS program (SAS version 9.3, SAS Institute Inc, Cary NC) with randomization performed in blocks of size N=6 to ensure that after every sixth patient is enrolled there are an equal number of patients assigned to each of the 3 treatment conditions. Using this randomization schedule, an EXCEL spreadsheet application will be created which will include sequentially assigned subject-ID numbers and corresponding treatment assignments. When a patient is enrolled they will be assigned the next sequential subject-ID number and a member of the anesthesia clinical research unit, who will be different from the care team and are not involved in the medical management of the patient, will use the online system to retrieve the allocated treatment assignment for this subject-ID.

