7.1 Sample Size Determination

The sample-size for this study was determined in order to provide statistical power of >90% to detect a difference of 3 units for the primary endpoint (OBAS on POD1). Based on a previous study, we hypothesize that the standard deviation of OBAS will be approximately 3 units.⁴⁴ Under this assumption, an effective sample-size of N=39 per group will provide statistical power of >90% to detect a difference between groups of 3 units using a two-sided, alpha=0.017 (multiple-comparison adjusted for 3 groups), non-parametric test. In addition, for the key secondary endpoint of pain (NRS), this sample-size will provide statistical power of 80% to detect a difference of 0.75 standard deviations (approximately 2.25 units on the NRS). In order to accommodate attrition of approximately 10% (due to canceled surgery, failed block, etc.) we propose a total sample-size of N=129 (43 patients per group).

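### As written, allocation can be retrieved before the day of surgery and before baseline NRS is recorded, so a cancelled case can be randomised with no possible OBAS; retrieve it on the day, after baseline.

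*Combined protocol and SAP*

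**What the plan says.** **Recruitment (4.3).** Coordinators meet eligible patients "at either their preoperative orthopedic appointment or the morning of surgery", the latter only for patients who are not first on the day's list. The same section treats the study staff and the clinical research unit as one group: "study staff/clinical research unit, which includes the research study coordinators".

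**Allocation (5.3).** "When a patient is enrolled they will be assigned the next sequential subject-ID number", and a member of the research unit "will use the online system to retrieve the allocated treatment assignment for this subject-ID". The trigger is enrolment; no date relative to surgery is given.

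**Baseline (6.1).** "Following informed consent and randomization, study staff will record baseline patient demographics". The list includes baseline NRS at rest, and the sources are the medical record, the patient interview, or both. SF-12 and ASES are scheduled as preoperative (3.3 and the activity table in 6.3), with no stated order relative to randomisation.

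**Attrition (7.1).** The step from 39 to 43 per group covers "attrition of approximately 10% (due to canceled surgery, failed block, etc".

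**Analysis set (7.3).** "any subject randomized into the study, regardless of whether they received study drug, will be included in the primary analysis".

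**Outcome and blinding.** OBAS is collected once, on POD 1 (6.3 table, 6.4). The trial is unblinded (5.7).

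**The concern.** Three consequences follow if the arm is retrieved at a clinic visit.

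1. Surgery may be cancelled after randomisation. The patient then belongs to the primary analysis set but can never have the primary outcome.
2. Nothing conceals the arm from the patient in the interval. The arms differ visibly: an awake block, a block with a catheter, or an injection under general anaesthesia. A patient who dislikes the assignment can leave before surgery. Section 4.4.1 gives voluntary withdrawals no follow-up, and 4.4.2 excludes data after withdrawal. Loss of that kind could differ by arm, which a larger sample does not cure.
3. A patient-reported baseline score obtained after allocation in an open trial may be coloured by the assignment, and the staff recording it belong to the unit that retrieves the arm.

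At stake are the integrity of the intention-to-treat comparison and the neutrality of baseline NRS.

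**Working it through.** **Step 1. Order of events as written.**

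| Step | Section | Timing stated |
|---|---|---|
| Approach and consent | 4.3 | Clinic appointment or morning of surgery |
| Arm retrieved | 5.3 | At enrolment; no date |
| Baseline, including NRS at rest, recorded | 6.1 | After consent and randomisation |
| SF-12, ASES | 3.3, 6.3 | Preoperative; order relative to the arm not stated |
| OBAS | 6.3, 6.4 | POD 1 only |

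Retrieval before the day of surgery follows from reading 4.3 and 5.3 together. It is permitted, not stated.

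**Step 2. Can a cancelled case be analysed?** Section 7.3 requires it. OBAS first exists on POD 1, so there is no value and no earlier value. The missing-data text in 7.2 adjusts only if thought necessary and reserves last observation carried forward for success rates. No method is specified that would bring the patient into the OBAS comparison.

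**Step 3. Does the baseline order reach the primary test?** Section 7.2 compares OBAS by ANOVA or Kruskal-Wallis without a baseline covariate, so it does not. The exposure is the baseline table and any change score formed from baseline NRS.

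**Step 4. Reproduce the plan's power.** Inputs from 7.1: OBAS difference 3 and SD 3, so d = 3/3 = 1; NRS d = 0.75; two-sided alpha 0.017; n = 39 per arm. I used the two-sample t-test with noncentrality d × √(n/2) and 2n − 2 degrees of freedom.

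- OBAS: 1 × √(39/2) = 4.416, critical value 2.440, power 97.4%. With the lower-bound Wilcoxon efficiency of 0.864 it is 94.8%. Both agree with the stated figure of more than 90%.
- NRS: 0.75 × √(39/2) = 3.312, power 80.6%, against the stated 80%.

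**Step 5. What later allocation could recover.** Budgeted loss is 43 − 39 = 4 per arm, or 12 of 129 (9.3%). The documents do not say how much of this falls between enrolment and surgery. I assume 2–8%: 129 × 0.02 = 2.6 and 129 × 0.08 = 10.3, so about 3 to 10 patients, or 1 to 3 per arm. Evaluable n becomes 40 to 42.

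| n per arm | OBAS power | NRS power (0.75 SD) |
|---|---|---|
| 39 | 97.4% | 80.6% |
| 40 | 97.7% | 81.7% |
| 42 | 98.3% | 83.9% |
| 43 (no loss at all) | 98.5% | 84.9% |

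The last row is not attainable through timing alone. Section 7.1 also counts failed blocks, and 4.4.1 counts patients terminated from the study; later allocation prevents neither.

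**The case against.** **Clinic randomisation is inferred.** Section 4.3 describes where patients are met, and 5.3 does not date retrieval. Some eligibility items in 4.2, such as the pre-procedural urine test and the anticoagulant holds, settle close to surgery, so the text also fits enrolment on the day. This stands: a reader might infer that patients are routinely randomised at clinic, and the documents do not say so. They do permit it. Because first cases are not approached on the morning of surgery, those patients must be met earlier.

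**Recording is not measuring.** Under 6.1, baseline values may come from the medical record and so predate allocation. No section says that the patient has been told the arm. This also stands: a reader might infer that all baseline scores are given with the arm known, but only an NRS taken at interview is plausibly exposed. For SF-12 and ASES the order is simply unstated.

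**The loss is already allowed for.** The 43 per arm covers it in numbers, and 7.2 plans to compare prognostic factors between patients with and without data. Both are true, but neither supplies a missing OBAS nor removes loss that depends on the arm.

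**Arm-related withdrawal is speculative.** It is a possibility, not something the documents show. Cancellation itself is not shown to depend on the arm. Nor would later allocation close the route fully: a patient told the arm on the day can still withdraw.

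**Conclusion.** The point holds as an inexpensive improvement to the order of steps. The conflict between 7.1 and 7.3 is in the text: cancelled surgeries are expected among those enrolled, every randomised patient is to be analysed, and a cancelled case cannot have an OBAS. Whether such cases are in fact randomised before cancellation depends on when the arm is retrieved, which the plan leaves open.

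The benefit is fewer avoidable losses after randomisation and less scope for bias; its size cannot be calculated from the documents. It is not a power argument. OBAS power is at least 97.4% from 39 per arm upward, and the NRS gain is from 80.6% to about 82–84%, resting on the assumed 2–8% pre-surgery loss and an even split across arms. The sample size stands.

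Two stronger conclusions are tempting and unsupported. One is that the primary comparison is biased by late baseline collection: the test uses no baseline value. The other is that retiming would recover the whole attrition allowance: part of it is for failed blocks and terminations, and 6.2 keeps failed blocks in the study anyway.

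**What to change.** Leave consent as planned. Amend 5.3 so that the allocation is retrieved only on the day of surgery, once surgery is confirmed and baseline NRS, SF-12 and ASES are complete. Amend 6.1 so that baseline recording comes before randomisation. A sentence in 7.3 should say how any remaining patient who is randomised but not operated on is counted, with numbers by arm.

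The cost is logistical. First cases of the day, consented at clinic, need retrieval early that morning, and block teams get shorter notice of the arm. Section 4.3 already allows patients later on the list to be approached that morning, so same-day processing is established for them; for first cases it would be new. No treatment, endpoint or sample size changes. The change does not prevent failed blocks or withdrawal after allocation on the day.
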